5.4 Duration of Therapy

In the absence of treatment delays due to adverse events, treatment will continue indefinitely or until one of the following criteria applies:

- Disease progression,
- Intercurrent illness that prevents further administration of treatment,
- Unacceptable adverse event(s),
- Patient decides to withdraw from the study, or
- General or specific changes in the patient's condition render the patient unacceptable for further treatment in the judgment of the investigator.

Prior to cycle 3, patients undergo clinical and radiographic tumor restaging. As long as the tumor is stable or smaller in size and the patient is clinically stable or improved, they will go on to another 2 four week cycles of therapy with temsirolimus and perifosine. Treatment will continue indefinitely as long as there are no unacceptable toxicities (DLTs) and no tumor progression.

5.5 Duration of Follow Up

Patients will be followed every 3 months for survival after removal from study. Patients removed from study for unacceptable adverse events will be followed until resolution or stabilization of the adverse event. They should then be followed for survival every 3 months.

5.6 Criteria for Removal from Study

Patients will be removed from study when any of the criteria listed in [Section 5.4](#) applies. The reason for study removal and the date the patient was removed must be documented in the Case Report Form.

6 DOSING DELAYS/DOSE MODIFICATIONS

6.1 Dose Modifications

Patients with stable or responding disease may be retreated at the same dose or at a reduced dose level, depending upon the adverse events observed in the current cycle and any adverse events present on the first day of the next cycle. If multiple toxicities are seen, the dose administered in a subsequent cycle should be based on the most

Amended:

Reviewed by OCR, JR 3/24/14

severe toxicity experienced in the current cycle. Dose modifications or delays should be made based upon whether toxicities occur within a 4-week treatment cycle or at the expected start of the next treatment cycle.

Patients who experience dose-limiting toxicity should have laboratory testing at least weekly until the toxicity has resolved.

6.1.1 Within Treatment Cycle:

If a patient experiences DLT (as defined in [Section 5.2](#)) during the current treatment cycle, the treatment will be immediately suspended for a minimum of 1 week. If the toxicity resolves to less than or equal to grade 1 (or to within 1 grade of starting values for pre-existing laboratory abnormalities) within 2 weeks of the last dose of both temsirolimus and perifosine (grade 2 for diarrhea and hyperlipidemia), the patient will be retreated at one or two dose levels lower (see [Section 6.1.2 - 6.1.5](#)). Patients experiencing DLT at the initial starting dose of temsirolimus of 15 mg i.v. weekly will have the dose reduced according to [Table 4](#). No dose reduction below 5 mg i.v. weekly is allowed. Otherwise, there is no limit on the number of dose level reductions. If temsirolimus-related toxicity persists at dose level -2 (5 mg i.v. weekly), the patient should be taken off study.

Doses that are reduced for temsirolimus or perifosine related toxicity will not be re-escalated, even if there is minimal or no toxicity with the reduced dose. Patients whose dose has been reduced for adverse events that are subsequently not felt to be related to temsirolimus or perifosine may have the dose re-escalated after completion of one cycle with toxicities less than or equal to grade 1. If any patient has further toxicities that would require additional reductions, or if treatment is held for more than 2 consecutive weeks because of ongoing toxicity, the investigator and the CTEP medical monitor will assess if the patient should remain in the study (if the patient has benefited from treatment).

Table 4: Temsirolimus Dose Modifications Table:

Dose Modifications	
Dose Level	Dose of Temsirolimus (mg/week intravenously)
Level -2	5 mg
Level -1	10 mg
Starting dose (Level 1)	15 mg
Level 2	25 mg
Level 3	50 mg
Level 4	75 mg
Level 5	115 mg
Level 6	170 mg

Table 5: Perifosine Dose Modifications Table for Maintenance Dose

Dose Modifications	
Dose Level	Dose of perifosine
Level -2	50 mg every other day

Amended:

Reviewed by OCR, JR 3/24/14

Level -1	50 mg per day
Starting dose (Level 1)	100 mg per day

6.1.2 Hematologic Toxicity

No dose adjustment or reduction of perifosine will be made for hematologic toxicity.

Dose Modifications of CCI-779 (Temirolimus) Based on Weekly ANC and Platelet Counts:

ANC (/mL)	Platelets (/mL)	% of Planned temsirolimus
≥ 1000	and ≥ 75,000	100%
750-999	or 50,000 to < 75,000	hold*
< 750	or < 50,000	hold**

* Upon recovery to ANC \geq 1,000/mL and platelets to \geq 100,000/mL, one lower dose level of temsirolimus will be administered (See [Table 4](#)). Patients already at the lowest dose level (5 mg i.v. weekly) will be removed from study.

** Upon recovery to ANC \geq 1,000/mL and platelets to \geq 100,000/mL, two lower dose levels will be administered. The exception will be patients at dose level -1 (10 mg i.v. weekly) who will be dose-reduced by only one level to 5 mg IV weekly (See [Table 4](#)). Patients already at the lowest dose level (5 mg i.v. weekly) will be removed from study.

6.1.3 Non-hematologic toxicity

Dose Modifications Based on perifosine and temsirolimus-related Non-Hematologic Toxicities and dose adjustments for each drug shown in [tables 4, 5, and 6](#):

NCI Grade	% of Planned perifosine and temsirolimus dose
0-2+	100%+
3*	hold**
4	hold***

- + For symptomatic Grade 2 toxicity, the dose may be held until recovery to CTC Grade 0-1, then continue at the same dose or reduce by one level of temsirolimus and/or perifosine at the investigator's discretion. Grade 2 diarrhea does not require temporary discontinuation of treatment as this toxicity may improve despite continued treatment. For grade 2 diarrhea that is unacceptable to the patient for symptomatic reasons, hold perifosine temporarily held until resolution \leq grade 1 and subsequently re-started at the same dose. If symptomatic grade 2 diarrhea recurs after re-instituting treatment at the same daily dose and require temporary discontinuation, treatment of both agents should be held until resolution to \leq grade 1 and re-instituted at a reduced doses of both agents (see [Table 4, 5, and 6](#)).
- + In addition, areas of intratumoral micro-hemorrhage were noted on necropsy of mice harboring modeled GBMs following combined treatment of perifosine and temsirolimus. Significance of this in humans is unclear, and it may represent an early response to therapy. However, for patient safety, a non-contrast head CT or MRI with gradient echo imaging is required during the 2nd week of therapy to evaluate for such microbleeds. CTCAE grade 1 (asymptomatic, radiographic findings only) do not require treatment modification. CTCAE grade 2 (medical intervention indicated) may require corticosteroids as treatment for associated edema or other intervention at the discretion of the investigator, but treatment can continue at the discretion of the investigator.

Memorial Sloan Kettering Cancer Center
IRB Protocol

IRB#: 09-058 A(14)

- * Except nausea/vomiting (unless patients are on maximal antiemetic therapy) or hypercholesterolemia and hypertriglyceridemia and other Metabolism and Nutrition Disorders (such as hypophosphatemia and hypocalcemia) unless remaining grade 3 or unacceptable grade 2, despite maximal medical therapy.
- ** Hold (no minimum time unless a DLT) until recovery to CTC Grade 0-1 (or to within 1 grade of starting values for pre-existing laboratory abnormalities), and then resume per [table 6](#). For diarrhea, and hyperlipidemia, hold until recovery to CTC grade 2, unless the patient cannot tolerate symptoms in which case the dose may be held until recovery to CTC Grade 0-1. Antilipid therapy should be initiated for hyperlipidemia such as with pravastatin (which dose not affect cytochrome metabolism), extended release niacin, or gemfibrozil (Lopid) (see 5.3.5 and 6.1.5). Note that Subjects with toxicities that are manageable with supportive therapy do not require dose reductions unless they remain grade 3 or unacceptable grade 2 despite maximal medical therapy.
- *** Hold (no minimum time unless a DLT) until recovery to CTC Grade 0-1 (or to within 1 grade of starting values for pre-existing laboratory abnormalities), and then resume per [table 6](#). The exception will be patients at dose level -1 of temsirolimus (10 mg i.v. weekly) who will be dose-reduced by only one level to 5 mg i.v. weekly. For diarrhea and hyperlipidemia, hold until recovery to CTC grade 2, unless the patient cannot tolerate symptoms in which case the dose may be held until recovery to CTC Grade 0-1. Antilipid therapy should be initiated for hyperlipidemia such as with pravastatin (which dose not affect cytochrome metabolism), extended release niacin, or gemfibrozil (Lopid) (see 5.3.5 and 6.1.5).

An important exception to this scheme are patients with symptoms suggestive of interstitial pneumonitis. Because pneumonitis is an anticipated toxicity for temsirolimus, patients with signs/symptoms of pneumonitis should have treatment held and be promptly evaluated. Those patients subsequently diagnosed with pneumonitis thought to be possibly related to study agent(s) should have treatment discontinued and be removed from study.

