5.2 Definition of Dose Limiting Toxicity

5.2.1 Definition of dose limiting toxicities (DLT):

Toxicities will be graded according to the CTCAE version 4.0. If multiple toxicities are seen, the presence of DLT should be based on the most severe toxicity experienced. DLT will be defined as any of the following events occurring during treatment with temsirolimus and perifosine and attributable (possible, probable, or definite) to either study drug or the combined therapy:

- Any grade 3 thrombocytopenia, grade 4 anemia, and/or grade 4 neutropenia.

Amended:

Reviewed by OCR, JR 3/24/14

- Any unacceptable grade 2 non-hematologic toxicity, despite maximal medical treatment, that results in dose interruption of greater than 7 days within the first 28 days.*
- Any non-hematologic grade 3 or 4 toxicity, excluding alopecia, despite maximal medical treatment.*
- Failure to recover from toxicities to be eligible for re-treatment with temsirolimus and perifosine within 2 weeks of the last dose of temsirolimus and perifosine.

*Non-hematologic toxicities diarrhea and mucositis will only be considered a DLT if they remain grade 3 or unacceptable grade 2, despite maximal medical therapy.

*Hypercholesterolemia and hypertriglyceridemia and other Metabolism and Nutrition Disorders (such as hypophosphatemia and hypocalcemia) will only be considered a DLT if they remain grade 3 or unacceptable grade 2, despite maximal medical therapy

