All other toxicities	Continue drug; no dose reduction	Hold drug and reduce dose per Section 6.1.3 and dose levels in table 4 except Subjects with toxicities that are manageable with supportive therapy do not require dose reductions unless they remain grade 3 or unacceptable grade 2 despite maximal medical therapy
----------------------	----------------------------------	--

6.1.4 At the Start of the Next Treatment Cycle:

Additional cycles of therapy may be administered provided that the patient meets the following criteria on Day 1 of each cycle (labs may be drawn up to 3 days before the start of the cycle):

- ANC \geq 1,000/mcL
- Platelets \geq 100,000/mcL
- Non-hematologic toxicity recovered to \leq grade 1 (or tolerable grade 2) EXCEPT
 - Non-hematologic toxicities such as rash, diarrhea and mucositis will only be considered a DLT if they remain grade 3 or unacceptable grade 2, despite maximal medical therapy.
 - *Hypercholesterolemia and hypertriglyceridemia and other Metabolism and Nutrition Disorders (such as hypophosphatemia and hypocalcemia) will only be considered a DLT if it remains grade 3 or unacceptable grade 2, despite maximal medical therapy.
- No evidence of progressive disease

In the event of toxicity, the doses of temsirolimus will be adjusted according to the guidelines shown in the Dose Delays/Dose Modifications [table7](#) below. If an adverse event is not covered in the table, doses may be reduced or held at the discretion of the investigator for the subject's safety. Dose adjustments for hematological toxicity are based on the blood counts obtained in preparation for the day of treatment.

Patients requiring dose reductions should not have the dose re-escalated with subsequent treatments.

Subjects with toxicities that are manageable with supportive therapy do not require dose reductions unless they remain grade 3 or unacceptable grade 2 despite maximal medical therapy: hyperlipidemia may be treated with statins, such as pravastatin (which does not affect cytochrome metabolism), extended release niacin, or gemfibrozil; nausea/vomiting may be treated with antiemetics; and diarrhea may be treated with loperamide rather than by dose reduction

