Subjects will be withdrawn from the study if they fail to recover to CTC Grade 0-1 or tolerable grade 2 (or within 1 grade of starting values for pre-existing laboratory abnormalities) from a treatment-related toxicity (EXCEPT toxicities that are manageable with supportive therapy as above) within 14 days from the last dose of both temsirolimus and perifosine OR they experience agent related adverse events requiring dose modification despite two previous dose reductions (i.e. would require a 3rd dose reduction) unless the investigator, PI, and CTEP monitor agree that the subject should remain in the study because of evidence that the patient is/may continue deriving benefit from continuing study treatment. The appropriate reduced dose will be determined after discussion between the principal investigator and CTEP monitor.

Amended:

Reviewed by OCR, JR 3/24/14

Table 7

Adverse Event	Agent	Treatment Modifications
Blood/Bone Marrow		
Grade 3: Neutrophils ANC 500-1000 Platelets 50,000-75,000	Temsirolimus	
 Delay Temsirolimus until recovery to \leq grade 1. Retreat at a one dose level reduction If recovery requires > 14 days from the last dose of both temsirolimus and perifosine, discontinue all study treatment.
Grade 4: Neutrophils ANC < 500 Platelets $< 25,000$		
 Delay Temsirolimus until recovery to \leq grade 1. Retreat at two dose levels reduction If recovery requires > 14 days from the last dose of both temsirolimus and perifosine, discontinue all study treatment.
Pulmonary/Upper Respiratory		
Pneumonitis (cough, dyspnea, fever)	Temsirolimus	Discontinue Temsirolimus pending investigation. If diagnosis is confirmed and events are considered at least possibly due to Temsirolimus, the agent is removed from the study.
All other non-hematologic adverse events except nausea, vomiting, and diarrhea		
Grade 0-2	Temsirolimus	Grade 2 toxicities that are persistent and intolerable (i.e. stomatitis) can result in dose delays and dose reductions to the next lower dose level
Grade 3-4		
Hold dose.
 
 Re-evaluate until AE resolved to \leq 1 or tolerable grade 2. Re-treat at a one dose level reduction If recovery requires > 14 days from the last dose of both temsirolimus and perifosine, discontinue all study treatment. Patients with grade 4 AEs related to agent may be taken off study at investigator's discretion.

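### Section 6 conflicts on whether perifosine is held for a grade 3-4 event or a DLT, and on whether pneumonitis takes the patient or only temsirolimus off study

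*Combined protocol and SAP*

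**What the plan says.** All references are to the combined protocol and SAP.

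- **Section 6.1.1 (within a cycle).** If a patient has a DLT, "the treatment will be immediately suspended for a minimum of 1 week". Retreatment requires recovery "within 2 weeks of the last dose of both temsirolimus and perifosine".
- **Section 5.2.1 (DLT definition).** DLTs include "Any grade 3 thrombocytopenia, grade 4 anemia, and/or grade 4 neutropenia". Failure to recover enough for retreatment within two weeks of the last dose of the two drugs is also a DLT.
- **Section 6.1.2 (hematologic).** "No dose adjustment or reduction of perifosine will be made for hematologic toxicity". Only temsirolimus is held on low counts.
- **Section 6.1.3 (non-hematologic).** The lead-in points to Tables 4, 5 and 6 for the adjustments to each drug. The grade table then has a single column, the percentage "of Planned perifosine and temsirolimus dose", with hold at grades 3 and 4. Its footnotes say to hold until recovery and then resume under Table 6. For certain toxicities, such as hyperlipidemia, the grade 3 hold applies only if the event persists despite maximal medical therapy.
- **Table 6 (summary by drug).** For perifosine the entry is "Continue drug; no dose reduction" for hematologic, rash, stomatitis, pulmonary, hepatic, hyperlipidemia and all other toxicities.
- **Pneumonitis.** Under 6.1.3, patients whose diagnosed pneumonitis is possibly related to study agents "should have treatment discontinued and be removed from study". In Table 7, whose agent column lists temsirolimus, a confirmed and possibly related case means "the agent is removed from the study".

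**The concern.** Two readers of section 6 can treat the same event in opposite ways and each cite the protocol. One stops daily perifosine with temsirolimus; the other stops temsirolimus alone. One takes a patient with pneumonitis off study; the other withdraws one drug.

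This concerns patient safety first, because the instruction applies when a serious toxicity has just occurred. It also affects the data. Perifosine exposure after a toxicity, time on study and the recovery rule in the DLT definition all depend on which drug was last taken and when.

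**Working it through.** The plan states no figure on this point, so there is nothing to reproduce. The check sets the instructions side by side and counts rows in Table 6.

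**Row count.** Table 6 has 9 toxicity rows.

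| Table 6 row | Perifosine | Hold of both drugs elsewhere |
|---|---|---|
| Hematologic | continue | 6.1.1, if the event is a DLT |
| Rash | continue | 6.1.3, grade 3-4 |
| Stomatitis | continue | 6.1.3, grade 3-4 |
| Pulmonary | continue | 6.1.3, grade 3-4 |
| Hepatic | continue | 6.1.3, grade 3-4 |
| Hyperlipidemia | continue | 6.1.3, grade 4 or persistent grade 3 |
| All other | continue | 6.1.3, grade 3-4 |
| Diarrhea, nausea, vomiting | hold | not counted |
| Joint pain/gout | hold | mismatch is on temsirolimus |

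The hematologic row lies outside 6.1.3, which leaves 9 - 1 = 8 non-hematologic rows. Two of these hold perifosine, so 8 - 2 = 6 continue it. In the joint pain/gout row the mismatch runs the other way: the 6.1.3 grade table holds both drugs, while Table 6 continues temsirolimus.

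**Conflict 1, non-hematologic grade 3-4.** The 6.1.3 column names both drugs and its entry is hold. The footnotes then resume dosing under Table 6. A drug that Table 6 never interrupts cannot be resumed under Table 6. The catch-all row makes this the default case.

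**Conflict 2, DLT.** Take a grade 3 thrombocytopenia attributed to treatment. Under 5.2.1 it is a DLT. Section 6.1.1 then suspends treatment for at least a week and counts recovery from the last dose of both drugs, which implies that both have stopped. Table 6 continues perifosine. Section 6.1.2 bars perifosine adjustment or reduction; those words alone might still allow a pause, so the sharper conflict is with Table 6.

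**Conflict 3, pneumonitis.** Section 6.1.3 removes the patient; Table 7 removes the drug. The Table 6 pulmonary row continues perifosine, but its temsirolimus cell refers back to 6.1.3, so it is weaker evidence of a third instruction.

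**Exposure.** At the phase I starting maintenance dose of 100 mg per day (5.1.1.5), perifosine taken under one reading and omitted under the other comes to:

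- 7 days × 100 mg = 700 mg
- 14 days × 100 mg = 1,400 mg

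Sections 5.1.1.5 and 5.1.1.6 also call for a repeat perifosine load after an interruption of more than 7 days, so the reading chosen can decide whether a second load is given.

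**Recovery clock.** The limits in 5.2.1, 6.1.1, 6.1.3.1, 6.1.4 and Table 7 run two weeks (14 days) from the last dose of both drugs. Suppose temsirolimus is held, perifosine continues daily, and the toxicity is unresolved 14 + 1 = 15 days after the last infusion. Counted from the last temsirolimus dose, 15 > 14 and the limit has passed. Counted from the more recent dose of either drug, at most 1 day has elapsed and the limit never arrives.

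**Link to the MTD.** An event that already meets another DLT criterion counts whatever happens to perifosine afterwards. The clock matters only where slow recovery is what would make the event a DLT. Grade 3 neutropenia is an example: it is not on the hematologic list in 5.2.1, temsirolimus is held for it, and perifosine continues under 6.1.2. Under 5.2.2 only the first 28 days count.

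**The case against.** The best defense is the lead-in to 6.1.3. It sends the reader to Tables 4, 5 and 6 for each drug, and Table 6 has one column per drug. On that reading 6.1.3 sets the grade that triggers action, Table 6 allocates the action by drug, and the shared column is just a loose heading. This is plausible and may be what was intended. It is not what the text says: the heading names both drugs, and hold-then-resume does not describe a drug that continues. The pointer also does not reach 6.1.1, and the 6.1.3 footnotes treat the DLT hold as a separate rule.

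Other parts of the defense stand:

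- Section 6.1.1 refers to the treatment and never says outright that both drugs stop. The both-drug reading comes from its recovery clock.
- Section 6.1.4 introduces Table 7 as adjusting temsirolimus, so silence there on perifosine is unsurprising. The patient's status after pneumonitis still differs from 6.1.3.
- Section 6.1.5 gives a contact for dose questions, and the study is at a single institution. That reduces inconsistency but does not supply a written rule.

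A reader might infer three firm and separate pneumonitis outcomes. The pulmonary row does not name pneumonitis and refers back to 6.1.3, so the firm conflict is between two places.

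A reader might also infer that the MTD or the efficacy result is broadly compromised. Later perifosine handling cannot undo a DLT already counted. On efficacy, section 11.2 leaves early removals for toxicity out of the six-month PFS set, so the off-study decision could matter there. But section 13.5.2 assesses everyone treated, and the documents show no effect on the result.

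**Conclusion.** The inconsistency is real and lies in current operative text. Perifosine is both held and continued for grade 3-4 events in 6 of the 8 non-hematologic rows of Table 6, and for hematologic DLTs. Confirmed pneumonitis possibly related to temsirolimus leads to removal of the patient in one place and of one drug in another.

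The consequence is limited but concrete: different perifosine exposure and a different off-study decision for the same event. The effect on DLT classification is confined to events that would be DLTs only through slow recovery.

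The conclusion rests on two readings: that the 6.1.3 heading means what it says, and that suspending treatment in 6.1.1 covers both drugs, as its clock implies. If the sponsor intended Table 6 to govern, the wording still needs correcting. This is a fault of consistency between passages, not a judgment on which rule is clinically right.

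**What to change.** Reconcile sections 6.1.1, 6.1.2 and 6.1.3 with Tables 6 and 7 so that:

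1. each toxicity and grade has one stated action for each drug, and it is clear which passage governs if two apply;
2. the suspension for a DLT says which drug or drugs it covers, including for hematologic DLTs;
3. pneumonitis has one outcome throughout, for each drug and for the patient's study status;
4. the recovery limits in 5.2.1 and section 6 say when the clock starts if only one drug is held.

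The sponsor decides the actions. The cost is amendment wording; sample size, endpoints and analysis are unchanged.
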